7.2 Conventions

Unless otherwise specified, the following conventions will be applied to all analyses:

- 1 year = 365.25 days. Year is calculated as (days/365.25) rounded up to 1 significant digit.
- 1 month = 30.4375 days. Month is calculated as (days/30.4375) rounded up to 1 significant digit.
- Age will be calculated by the following SAS code: age = floor(yrdif(birth_date, consent_date, 'AGE'))
- 1 pound = 0.454 kg
- 1 inch = 2.54 cm
- Missing safety data will not be imputed unless otherwise specified.
- For laboratory results collected as < or > a numeric value, 0.000000001 will be subtracted or added, respectively, to the value.
- For safety analyses, percentages will be calculated based on the number of patients in the analysis population.
- For by-visit observed data analyses, percentages will be calculated based on the number of patients with nonmissing data as the denominator unless otherwise specified.
- For other continuous endpoints, the summary statistics will include mean, standard deviation, median, and range (minimum and maximum).
- For categorical endpoints, the summary statistics will include counts and percentages.
- AEs and medical history will be coded using the Medical Dictionary for Regulatory Activities (MedDRA) version 17 or higher.
- Prior therapies and concomitant medications will be coded using the World Health Organization (WHO) Drug Dictionary version 201506.

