9.6.4 Time to Objective Response

The time to response (TOR) will be defined as the time from the first dose of SD-101 until the onset of CR or PR. TOR will be summarized descriptively for patients who achieved CR or PR.

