9.6.5 Duration of Response

The duration of response is defined as the period of time from the date of initial confirmed PR or CR until the date of PD or death, whichever is earlier. For those patients who achieved response, duration of response will be summarized descriptively. Kaplan-Meier estimate of median duration and 95% confidence interval will be provided.

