9.6.6 Progression-Free Survival

The progressive-free survival (PFS) is defined as the period of time from baseline to confirmed PD or death. Administration of palliative radiation therapy will be considered clinical progression for the purposes of determining PFS. The proportion of patients who had PFS at the end of the study will be summarized and PFS will be analyzed by Kaplan-Meier method; 95% confidence interval for the median will be provided. Overall survival (OS) is defined as the period of time from baseline to death, and analysis of OS will also be provided similarly as PFS.

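### SAP 7.2 rounds months and years upward to one significant digit; any duration converted by that rule is overstated, and about 10 to 20 months all become 20

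*SAP*

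**What the plan says.** SAP 7.2 (Conventions) opens with its scope: "Unless otherwise specified, the following conventions will be applied to all analyses". Two of the conventions concern durations. For months: "Month is calculated as (days/30.4375) rounded up to 1 significant digit". For years: "Year is calculated as (days/365.25) rounded up to 1 significant digit". Age is not covered by the year rule, because 7.2 gives it separate code.

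The durations that could be converted are defined in SAP 9.6.4 to 9.6.6:

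- Time to response is "the time from the first dose of SD-101 until the onset of CR or PR", summarised descriptively.
- For duration of response, "Kaplan-Meier estimate of median duration and 95% confidence interval will be provided".
- For PFS, "PFS will be analyzed by Kaplan-Meier method; 95% confidence interval for the median will be provided". The same subsection adds a binary summary: "The proportion of patients who had PFS at the end of the study will be summarized".
- "Overall survival (OS) is defined as the period of time from baseline to death", with OS analysed in the same way as PFS.

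None of these subsections gives a time unit or a display precision, makes an exception to 7.2, or says whether estimation is done on days or on converted values.

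**The concern.** One significant digit keeps only the leading digit of a number. Rounding upward then moves every value that is not already exact to the next leading digit. Below 10 months the step is a whole month; from 10 months onward it is ten months. A programmer who followed 7.2 as written would produce durations that are always too long and, beyond 10 months, almost without information.

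The rule is also worded as part of how a month or year is calculated, not as a display format. If it were applied to each patient's time before estimation, many times would be tied, and a Kaplan-Meier median could land only on the rounded values.

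The practical stake is comparison with outside results. Protocol 2.1.1 quotes median PFS for comparator regimens in months to one decimal place, for example 2.7, 2.8, 2.9 and 11.5. Under the literal rule the first three all become 3 and the last becomes 20. Trial medians produced that way could not be set beside those figures.

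**Working it through.** The plan states no result that depends on this rule, so there is no figure to reproduce. The check is to apply the rule to durations that the trial can generate.

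**Inputs**

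- Divisors 30.4375 and 365.25 (SAP 7.2). They agree with each other: 365.25/12 = 30.4375.
- Scan schedule (Protocol 8.2.1.2): first post-baseline scan on Day 64, then every 9 weeks to Day 379, then every 12 weeks. Counted from Day 1, the elapsed days are 63, 126, 189, 252, 315, 378, 462, 546, 630 and 714.
- Participation of up to about 110 weeks (Protocol 4.2): 110 × 7 = 770 days.

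**Formulas**

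Months = days/30.4375. Literal rule: round up to the next value with one significant digit. Alternative reading: round up to the next 0.1.

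**Results on the scan schedule**

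| Elapsed days | Months, exact | Literal rule | Change | Up to 1 decimal | Nearest 1 decimal |
|---|---|---|---|---|---|
| 63 | 2.07 | 3 | +45% | 2.1 | 2.1 |
| 126 | 4.14 | 5 | +21% | 4.2 | 4.1 |
| 189 | 6.21 | 7 | +13% | 6.3 | 6.2 |
| 252 | 8.28 | 9 | +9% | 8.3 | 8.3 |
| 315 | 10.35 | 20 | +93% | 10.4 | 10.3 |
| 378 | 12.42 | 20 | +61% | 12.5 | 12.4 |
| 462 | 15.18 | 20 | +32% | 15.2 | 15.2 |
| 546 | 17.94 | 20 | +11% | 18.0 | 17.9 |
| 630 | 20.70 | 30 | +45% | 20.7 | 20.7 |
| 714 | 23.46 | 30 | +28% | 23.5 | 23.5 |

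The change is the literal value divided by the exact value, minus 1; for 315 days, 20/10.349 = 1.93. Using the study-day label (64, 127 and so on) instead of elapsed days gives the same literal values.

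**Every whole-day duration from 1 to 770 days, literal rule**

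- No duration is left unchanged, in months or in years.
- Durations from 305 days (10.02 months) to 608 days (19.98 months) all become 20. The four scans from 10.35 to 17.94 months fall inside this band.
- The largest inflation factor is 2.00, at 305 days: 20/10.02. The unweighted mean factor over the range is 1.27; it weights each day equally and does not predict the bias in any endpoint.
- In years, 378 days (378/365.25 = 1.03) becomes 2.

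**Same range, upward to one decimal place**

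The largest excess is 0.0998 month, or 0.0998 × 30.4375 = 3.0 days.

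**The case against.** The strongest reply is that the extreme figures rest on an unlikely reading. One significant digit is plausibly a slip for one decimal place, and a table in which everything from 10 to 20 months reads 20 would probably be caught in output review. On the one-decimal reading the error is at most about 3 days, which is the size of the ±3-day imaging window and small against a 9-week scan interval. This has weight, but it is an inference: nothing in the SAP corrects the wording, and the upward direction would still be a one-sided bias.

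A reader might infer that every time-to-event result in the trial will be inflated. The documents do not support that. SAP 9.6.4 to 9.6.6 set no unit, so the endpoints may be reported in days, and 7.2 yields to other specifications. SAP 9.0 places table, graph and listing specifications in a separate document, which was not available here and may set unit and precision.

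A reader might also infer that rounded times enter the Kaplan-Meier estimate and create ties. The SAP does not say so. Estimating on days and converting the median afterwards fits the text equally well.

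Finally, the effect on decisions is limited. The Phase 2 primary endpoint is the objective response rate, a proportion that this rule cannot touch. The SAP plans descriptive analyses with no pre-specified testing. Protocol 4.3.2.2 stops collection of time to response, duration of response and PFS as of Amendment 9. The SAP still plans to analyse these endpoints, so that last fact reduces the point without removing it.

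**Conclusion.** The convention is wrong as written and should be corrected. Taken literally, it overstates any duration within the trial's length that is converted to months or years: by 9% to 93% at the protocol's scan times, with one value for everything from 305 to 608 days. If one decimal place was intended, the upward bias is under 0.1 month and of little practical importance.

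The harm is conditional. It reaches time to response, duration of response, PFS and OS only if they are expressed in months or years by this rule. Results kept in days, the objective response rate, the disease control rate and the proportion progression-free at end of study are unaffected. The percentages at scan times assume elapsed time counted from Day 1 and scans on the scheduled day.

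**What to change.** Amend the two lines in SAP 7.2 along these lines: months are days/30.4375 and years are days/365.25, kept unrounded in all derivations and estimation; displayed summary statistics are rounded half up to one decimal place. Estimating on days and converting the result is equally acceptable, provided that the SAP says which is done.

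In 9.6.4 to 9.6.6, state the reporting unit for time to response, duration of response, PFS and OS. Check that the separate table specifications use the same unit, precision and stage of rounding.

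The cost is two revised lines and a unit statement in three subsections. The protocol, data collection and sample size do not change.

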7.3 Rules for Missing Data

Missing data will not be imputed, except for missing date information for AEs and concomitant medications. The imputed dates will be used to determine the treatment-emergent period. For AEs with a partial date, available date parts (year, month, and day) of the partial date will be compared with the corresponding date components of the start date and end date of the treatment-emergent period to determine if the event is treatment emergent. When in doubt, the AE will be considered treatment emergent by default. The following rules will be applied to impute partial dates for AEs:

- If start date of an AE is completely or partially missing, impute as follows:
 - If both month and day are missing and year = year of first dose date, then set to first dose date.
 - If both month and day are missing and year \neq year of first dose date, then set to January 1.
 - If day is missing and month and year = month and year of first dose date, then set to first dose date.
 - If day is missing and month and year \neq month and year of first dose date, then set to first of the month.
 - If start date is completely missing and AE end date is on or after the first dose date, set to first dose date.
 - If start date is completely missing and AE end date is prior to the first dose date, do not impute an AE start date.
- If end date of an AE is partially missing, impute as follows:
 - If both month and day are missing, then set to December 31.
 - If only day is missing, then set to last day of the month.
 - If end date is completely missing, do not impute.

When the start date or end date of a medication is partially missing, the date will be imputed to determine whether the medication is prior or concomitant (or both). The following rules will be applied to impute partial dates for medications:

- If start date of a medication is partially missing, impute as follows:
 - If both month and day are missing, then set to January 1.
 - If only day is missing, then set to the first of the month.
- If end date of a medication is partially missing, impute as follows:
 - If both month and day are missing, then set to December 31.
 - If only day is missing, then set to last day of the month.
- If start date or end date of a medication is completely missing, do not impute.

Listings will show the original date information without imputation, but derived parameters (TEAE indicator and duration of AE) will be flagged to indicate the type of imputation performed.

8.0 TIMING OF ANALYSES

Final analyses will be carried out after the last participant has completed their last trial visit, the trial database has been authorized by Dynavax as complete and final, and major protocol deviations have been identified. No interim analysis is planned for this study.

9.0 STATISTICAL METHODS

This trial is designed to allow preliminary assessments of safety, biological activity, and biomarkers. No pre-specified hypothesis testing will be performed. All analyses of demographics, safety, biological activity, and biomarkers will be descriptive.

Efficacy and safety data will be analyzed and reported separately by Phase 1 dose group or Phase 2 analysis group.

Descriptive statistics, including the number of patients (n), mean, standard deviation (SD), median, minimum, and maximum, will be used to summarize continuous variables. Categorical variables will be summarized by number (n) and percentage (or proportions) of patients in each category. All data processing, summarization, and analyses will be performed using SAS Version 9.3 or higher. Specifications for tables, graphs, and data listings will be provided in the tables, figures, listings (TFL) specifications document.

9.1 Patient Disposition

Patient disposition will be summarized for all enrolled patients by dose or analysis group including patients in the safety, evaluable and ITT populations and patients discontinuing the study along with the reasons for discontinuation (as documented on the case report form study exit status).

A listing of patients discontinuing the study after enrollment will be produced.

9.2 Protocol Deviations

Patient data will be reviewed for major protocol deviations by the Medical Monitor prior to database lock. A listing of patients with major protocol deviations will be provided, sorted by treatment and describing their deviations. Any exclusions from analysis populations due to protocol deviations will be highlighted.

9.3 Demographics and Baseline Characteristics

Summary statistics for age, weight, height, body mass index at baseline, sex, race, and ethnicity will be presented by dose or analysis group for the safety, evaluable and ITT populations.

Listings will be provided for these parameters for all patients.

9.4 Prior and Concomitant Medications

Prior and concomitant medications will be coded using the World Health Organization (WHO) Drug Dictionary (version 201506). Prior medications are drugs and therapies used before the first dose date. Medications or therapies are considered concomitant if exposure occurs after the first dose date. The number and percentage of patients with concomitant medications will be presented alphabetically by anatomical therapeutic chemical (ATC) class and by decreasing order of frequency of preferred terms within each ATC class for the safety population. Patients taking the same medication multiple times will be counted once per medication.

All medications recorded on the case report form will be listed.

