7.5 Permitted Therapy

Topical or inhaled or intranasal corticosteroids (with minimal systemic absorption) and non-absorbed intra-articular steroid injections are permitted to treat AEs and may be continued with permission of the Dynavax Medical Monitor. Systemic corticosteroids required for the control of infusion reactions or immune-related AEs must be tapered and be at non-immunosuppressive doses (≤ 10 mg per day of prednisone or equivalent) before the next administration of SD-101 or pembrolizumab. A brief (< 24 hours) course of steroids for prophylaxis against contrast dye allergy is permitted for patients undergoing tumor assessments per institutional standard. Guidelines for steroid use to treat immunologic AEs are listed in Section 7.7.

Acetaminophen (maximum 3 g per day), ibuprofen, and/or ondansetron may be used post-SD-101 treatment to treat flu-like symptoms and pre-dose as prophylaxis. Pre- and post-SD-101 treatment prophylaxis with these agents is allowed but not encouraged for the first SD-101 dose for a patient in Phase 1 unless recommended per the Dynavax Medical Monitor. The sponsor may make further recommendations with regards to prophylaxis treatments for potential flu-like symptoms as the study is ongoing. See Section 9.3 for additional details.

Efforts should be made to keep all other concurrent medications at stable doses during the trial and to refrain from starting any new medications, unless clinically indicated. Therapy to prevent or treat local and/or systemic reactions following administration of either trial drug may include analgesics, antipyretics, and antihistamines.

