10.3.6 Safety Laboratory Assessments

Laboratory assessments are listed below and will be performed according to the Schedule of Trial Events ([Appendix 1](#) through [Appendix 4](#)). Sample collections prior to injection and infusion on treatment days are preferred; however, these samples are allowed to be obtained the day prior to dosing. Routine laboratory tests (serum chemistry, hematology) for screening, including pregnancy testing may be obtained per standard of care and used for screening laboratory and determination of study eligibility as long as obtained within 28 days of first dose of pembrolizumab. Laboratories obtained within 7 days of Day 1 visit, with the exception of a CBC with ANC, do not need to be repeated on Day 1.

- Hepatitis and HIV testing at Screening Visit: serum hepatitis B, hepatitis C, and HIV testing per institutional standard of care as determined by laboratory tests for HBsAg, anti-HBc, and anti-HBs; anti-HCV; and anti-HIV -1/2, respectively

- Chemistry: sodium, potassium, chloride, bicarbonate, blood urea nitrogen (BUN), creatinine, glucose, calcium, AST, ALT, LDH, bilirubin, alkaline phosphatase, and C-reactive protein (CRP)
- Hematology: hemoglobin, hematocrit, white blood cell count with differential, and platelet count
- Thyroid function tests: free T3, free T4, and thyroid stimulating hormone (TSH)
- Coagulation: PT and aPTT
- Reserve serum aliquot specimens will be collected and stored frozen for possible future testing.
- Urinalysis with microscopy

Additional details for specific tests are provided in the Laboratory Manual.

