7.0 DEFINITIONS, COMPUTATIONS, AND CONVENTIONS

7.1 Definitions and Computations

Study Day

Study day will be calculated in reference to the date of first dose (Day 1). For assessments conducted on or after the first dose date, study day is calculated as (assessment date – first dose date + 1). For assessments conducted before the first dose date, study day is calculated as (assessment date – first dose date). There will be no Day 0.

Date of First Dose and Date of Last Dose of Study Drug

The date of the first dose of study drug is defined as the date a patient receives the first dose of the study drug. The date of the last dose of study drug is the date a patient receives the last dose of the study drug.

Treatment-Emergent Period

Treatment-emergent periods are updated from what were described in the protocol (sections 10.3.9 and 10.3.10) to cover the maximum possible reporting periods.

Treatment-emergent period for AEs is defined the date and time of the first dose of study drug administration through 90 days after last dose of study drug administration.

Treatment-emergent period for SAEs is defined as the date and time of the first dose of study drug administration through EOS.

Baseline Value and Post-baseline Value

Unless otherwise specified, the baseline value is defined as the last measurement before the first dose (date and time) of study drug. Post-baseline value is defined as a measurement taken after the first dose of study drug. Change from baseline is defined as (post-baseline value – baseline value). Both date and time of study drug administration and measurement

will be considered when calculating baseline value. If time is not available, then date only will be used.

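### Under SAP 9.4 a medication used only on the first dose date is neither prior nor concomitant, so it is missing from the concomitant medication table

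*SAP*

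**What the plan says.** SAP 9.4 gives two definitions. For prior use: "Prior medications are drugs and therapies used before the first dose date". For concomitant use: "Medications or therapies are considered concomitant if exposure occurs after the first dose date". Only concomitant medications are tabulated, on the safety population, with each patient counted once per medication. Every medication on the case report form is also listed.

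SAP 7.3, on partial medication dates, foresees three outcomes: prior, concomitant, or both.

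SAP 7.1 treats measurements differently, using the clock as well as the calendar: "the baseline value is defined as the last measurement before the first dose (date and time) of study drug". Its counterpart is: "Post-baseline value is defined as a measurement taken after the first dose of study drug". For records without a time it adds: "If time is not available, then date only will be used". No rule follows for an untimed record dated on the day of first dose.

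On what may be given around dosing, Protocol 7.5 says that acetaminophen, ibuprofen and ondansetron "may be used post-SD-101 treatment to treat flu-like symptoms and pre-dose as prophylaxis". Protocol 9.3.2 describes infusion reactions as arising during or soon after the infusion and generally resolving within 24 hours. Its Table 9-1 names antihistamines among the possible treatments from Grade 2, and corticosteroids and epinephrine at Grades 3 and 4. Protocol 10.3.11 requires all such medications to be recorded.

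**The concern.** The two medication rules should together cover every recorded drug, with overlap allowed. As written they leave out one day, and it is the day on which a reaction to the first dose would be treated. In Phase 1 and in Cohorts 2 and 4 to 8 both drugs start on Day 1. In Cohorts 1 and 3 Day 1 carries pembrolizumab alone, so an infusion reaction is the relevant case there.

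What is at stake is the completeness of one descriptive safety table. A reader using it to see what was given for first-dose reactions would miss one-off, same-day treatment. Elsewhere the SAP includes the boundary: study day (7.1) and the rule for completely missing AE start dates (7.3) both count from the first dose date inclusive. The omission in 9.4 therefore looks like a slip.

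The baseline wording in 7.1 raises a lesser question. Two programmers could handle an untimed Day 1 value differently, and both could claim to follow the text.

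**Working it through.** No sample size, power or error rate enters, and the plan states no figure to reproduce. The check applies the rules to test records.

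**Medications.** Set the first dose date to Day 1, with no Day 0 (SAP 7.1). As written:
- prior: first use < Day 1
- concomitant: last use > Day 1

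With the boundary closed, concomitant becomes last use ≥ Day 1.

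| Use of the drug | Prior | Concomitant, as written | Concomitant, boundary closed |
|---|---|---|---|
| Day -5 to Day -1 | yes | no | no |
| Day -5 to Day 1 | yes | no | yes |
| Day 1 only | no | **no** | yes |
| Day 1 to Day 2 | no | yes | yes |
| Day 2 to Day 3 | no | yes | yes |
| Day -5, ongoing | yes | yes | yes |

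The third row is the gap: 1 < 1 is false and 1 > 1 is false. SAP 7.3 does not rescue it, because its imputation applies only to partial dates. Closing the boundary changes one other row: a drug begun earlier and stopped on Day 1 goes from prior only to prior and concomitant. That is correct, since the patient was exposed on the day of dosing.

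**When the gap alters the table.** The table counts patients per medication, so a count changes only if every on-study use of that drug by that patient falls on Day 1. Take the permitted uses in turn:
- Flu-like symptoms: Protocol 9.3 describes treatment, and continuation of prophylaxis, for 24 to 48 hours. Such a course reaches Day 2 and is captured.
- Infusion reaction treated the same day: not captured unless the drug is used again. After a Grade 2 reaction, Table 9-1 allows antihistamine premedication at later doses, which would restore the count. After Grade 3 or 4 it specifies no subsequent dosing, so later use is less likely to do so.

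**Baseline.** Take a first dose at 10:00 on Day 1.

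| Record | Result under SAP 7.1 |
|---|---|
| Day -3 | eligible as baseline |
| Day 1, 08:00 | eligible as baseline |
| Day 1, 12:00 | post-baseline |
| Day 1, no time | neither if date-only means strictly earlier; baseline if it means on or before |
| Day 8 | post-baseline |

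Only the untimed Day 1 row is undecided.

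**The case against.** The strongest reply on medications is that little is lost. SD-101 is planned for up to 11 doses in Phase 1, 22 in Cohorts 1 to 4 and 20 in Cohorts 5 to 8, so a patient who needs a symptomatic drug on Day 1 will often take it again and be counted. Protocol 7.5 does not encourage prophylaxis for the first SD-101 dose in Phase 1, and the listing keeps every record. All of this stands and limits the size. It does not close the gap for a drug used on Day 1 and never again. A reader might infer that the rule drops treatment for first-dose reactions in general; the 24-to-48-hour courses and the once-per-patient count show that it does not.

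On baseline, a reader might infer that an untimed Day 1 blood count is certain to be discarded and replaced by a screening value up to 28 days old. The documents do not support that:
- Time matters only for records dated on the day of dosing, so the date-only sentence exists for exactly these values. Reading it as on or before is at least as natural as reading it as strictly before.
- Timed Day 1 samples classify correctly. Protocol 10.2 requires procedure times in the trial records or a worksheet, although it does not say that they reach the database.
- Protocol 10.3.6 and 7.1 allow sampling the day before dosing, which gives a recent baseline with no tie.

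Nor is the blood count the only laboratory test due on Day 1. Protocol 10.3.6 says that laboratories within 7 days of Day 1, "with the exception of a CBC with ANC, do not need to be repeated on Day 1". Other tests are excused only if done within those 7 days, and the Phase 1 schedule lists chemistry, coagulation and urinalysis on Day 1.

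**Conclusion.** The medication point holds as a literal consequence of SAP 9.4: a drug used only on the first dose date is in neither class and is absent from the concomitant table, while remaining in the listing. This assumes that the first dose date is the date of whichever trial drug was given first, and that the rule is programmed as written.

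The size is small and cannot be computed, because the documents do not give the frequency of Day-1-only use. No response, dose-limiting toxicity or survival result is touched.

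The baseline point is an ambiguity confined to untimed values dated on the first dose date, not an error that must occur. It deserves a clarifying sentence because neutrophils, lymphocytes and platelets are summarized as change from baseline (SAP 9.7.4) and laboratory listings will not be produced, so a reader could not see which value had been used.

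**What to change.** 1. In SAP 9.4, define a medication as concomitant if exposure occurs *on or after* the first dose date. Leave the prior definition as it is; a drug may be both, as SAP 7.3 already allows.
2. In SAP 7.1, add to the date-only fallback that an untimed, protocol-scheduled pre-dose assessment dated on the first dose date is taken as pre-dose and is eligible as baseline.

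The cost is two sentences in the SAP and the matching lines of the derivation programs. No new data are needed. Besides closing the two gaps, the only change among the cases tested is that a drug stopped on Day 1 becomes concomitant as well as prior.
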